FDAAA	Food and Drug Administration Amendments Act of 2007
FFR	Federal Financial Report
GCP	Good Clinical Practice
GLP	Good Laboratory Practices
GMP	Good Manufacturing Practices
GWAS	Genome-Wide Association Studies
HIPAA	Health Insurance Portability and Accountability Act
IB	Investigator's Brochure
ICH	International Conference on Harmonisation
ICH E6	International Conference on Harmonisation Guidance for Industry, Good Clinical Practice: Consolidated Guidance
ICMJE	International Committee of Medical Journal Editors
IDE	Investigational Device Exemption
IND	Investigational New Drug Application
IRB	Investigational Review Board
ISO	International Organization for Standardization
LSMEAN	Least Squares Means
MedDRA	Medical Dictionary for Regulatory Activities
MOP	Manual of Procedures
MSDS	Material Safety Data Sheet
NIH	National Institutes of Health
NIH IC	NIH Institute & Center
OHRP	Office for Human Research Protections
PI	Principal Investigator
QA	Quality Assurance
QC	Quality Control
SAE	Serious Adverse Event
SAP	Statistical Analysis Plan
SMC	Safety Monitoring Committee
SOC	System Organ Class
SOP	Standard Operating Procedure
UP	Unanticipated Problem
US	United States

STATEMENT OF COMPLIANCE

The trial will be conducted in accordance with the ICH E6, the Code of Federal Regulations on the Protection of Human Subjects (45 CFR Part 46), and the <NIH IC> Terms of Award. The Principal Investigator will assure that no deviation from, or changes to the protocol will take place without prior agreement from the sponsor and documented approval from the Institutional Review Board, except where necessary to eliminate an immediate hazard(s) to the trial participants. All personnel involved in the conduct of this study have completed Human Subjects Protection Training.

I agree to ensure that all staff members involved in the conduct of this study are informed of their obligation to meet the above commitments.

Principal Investigator: _____
Print/Type Name

Signed: _____ Date:_____

STUDY SUMMARY

Title: A single arm phase II study of Cemiplimab-rwlc in immunocompromised patients with unresectable locally recurrent and/or metastatic cutaneous squamous cell carcinoma (CSCC)

Primary Objective: Determine the overall response rate of Cemiplimab-rwlc in immunocompromised patients with unresectable locally recurrent and/or metastatic CSCC.

Secondary Objective:

1. Evaluate progression-free survival
2. Evaluate overall survival
3. Evaluate acute and late toxicities

Exploratory Objective:

1. Identify potential biomarkers related to response to Cemiplimab-rwlc in immunocompromised patients with unresectable locally recurrent and/or metastatic CSCC.
2. Evaluate overall response rate of underlying chronic lymphocytic leukemia (CLL) in the CLL subset.

Primary Endpoint: Overall response rate of CSCC

Secondary Endpoint:

1. Progression-free survival
2. Overall survival
3. Acute and late immune-related and non-immune-related toxicities

Exploratory Endpoint:

1. Predictive biomarkers of Cemiplimab-rwlc response in CSCC
2. Overall response rate of underlying CLL in the CLL subset

Population: Immunocompromised patients with unresectable locally recurrent and/or metastatic CSCC.

Sample size: 27 patients.

Study groups: immunocompromised patients with unresectable locally recurrent and/or metastatic CSCC

Phase: Phase II

[figure not shown]
Number of Sites enrolling participants: 6

Description of Study Agent: Cemiplimab-rwlc

Study Duration: 24 months

Treatment Duration: 12 months

SCHEMA OF STUDY DESIGN

2 INTRODUCTION: BACKGROUND INFORMATION AND SCIENTIFIC RATIONALE

2.1 BACKGROUND INFORMATION

The incidence of cutaneous squamous cell carcinoma (CSCC) is increasing, and the estimated annual number of deaths due to CSCC is thought to be under reported.¹ The major risk factor for development of CSCC is exposure to UV radiation, particularly for fair-skinned people in geographic locations with high levels of UV radiation.^{2,3} In addition, chronic immunosuppression, advanced age, exposure to ionizing radiation, manufacturing chemicals, arsenic, chronic ulcers, and burn scars are also risk factors to develop CSCC.^{1,4} The majority of primary CSCC is treated surgically with or without post-operative radiation therapy depending on the risk of recurrence, and more than 95% of the patients are cured.^{1,4,5}

Although it is a highly curable cancer, some patients present with metastasis or locally advanced CSCC that are no longer amenable to surgery or radiation therapy. Unfortunately these patients are no longer curable, and their only option is palliative therapy. Among these incurable patients, immunocompromised patients have even worse clinical outcomes. For example, the 2-year progression free survival of immunocompromised patients excluding solid organ transplantation is only 27% in a retrospective study.⁶ In patients with no lymph node involvement but immunocompromised due to chronic lymphocytic leukemia, the locoregional failure rate is 36% even when they are treated aggressively with radiation postoperatively.^{7,8} Therefore, this patient population with an extremely poor prognosis needs improved treatment.

While immunocompromised patients have the most need for novel treatment options, they are often excluded in clinical trials. Recently, the programmed cell death-1 (PD-1)/programmed cell death-ligand 1 (PD-L1) axis was determined to play an important role as immune checkpoint. PD-1 is one of the clinically significant checkpoint molecules that has been shown to suppress T-cell function upon binding to its ligands, PD-L1 and PD-L2, which are expressed on tumor cells in both preclinical models and clinical settings of cancer patients undergoing immunotherapy.^{9,10} In addition to promising efficacy, PD-1 and PD-L1 inhibitors are overall safe and well tolerated in a subset of immunocompromised patients such as patients with HIV infection, and additional studies are currently ongoing.^{11,12} Immunotherapy targeting PD-1 has become a promising therapeutic option in management of CSCC.⁴ Cemiplimab-rwlc is one of the PD-1 inhibitors with the most efficacy and safety data in management of unresectable locally advanced or metastatic CSCC.⁴ With Cemiplimab-rwlc as a monotherapy in patients with metastatic CSCC, overall complete response rate is 7% and partial response rate is 41%. It also has a very favorable toxicity profile. Based on these efficacy and safety data, Cemiplimab-rwlc is now FDA approved for the treatment of patients with metastatic CSCC or locally advanced CSCC who are not amenable to curative surgery or curative radiation.¹³ However, immunocompromised patients were excluded in the Cemiplimab-rwlc trial, and the safety and efficacy of Cemiplimab-rwlc is unknown in this patient population with the most limited treatment options.

Even though it is counter intuitive to use immunotherapeutic approaches to immunocompromised patients, the full mechanism of how PD-1 inhibitors exerts anti-tumor effects are still unknown. In addition, recent data suggest that tumors with high tumor mutation burden respond better to PD-1 inhibitors because of increased presence of neoantigens.^{14,15} Chung, et al. evaluated 1,300 mucosal head and neck SCC, 2,386 lung SCC, and 289 CSCC for tumor mutation burden and found CSCC has the highest number of mutations per megabase among the squamous cell carcinomas from various organ sites.¹⁶ Therefore, it is important to evaluate the efficacy and toxicity of Cemiplimab-rwlc in immunocompromised CSCC patients.

2.2 RATIONALE

It suggests that CSCC is expected to be extremely sensitive to PD-1 inhibiting agents. However, there is no efficacy data in any immunocompromised population due to exclusion of these patients in clinical trials using PD-1 inhibitors. This population specific data are required to fulfill the unmet need.

2.3 POTENTIAL RISKS AND BENEFITS

2.3.1 KNOWN POTENTIAL RISKS

Cemiplimab-rwlc has not been tested in pregnant women, and there is no information available on patients receiving Cemiplimab-rwlc while pregnant. There is the possibility of unforeseeable risk to both the pregnant woman and unborn child if exposed to Cemiplimab-rwlc during pregnancy.

The most common side effects related to Cemiplimab-rwlc treatment are as follows:

Possible side effects:

Very Common (10% or more of patients):

- Fatigue
- Rash
- Nausea

Common (1 to ≤10% of patients):

- Arthralgia (joint pain)
- Diarrhea
- Decreased appetite
- Asthenia (weakness or lack of energy)
- Myalgia
- Vomiting
- Itching
- Underactive or overactive thyroid gland (which can cause tiredness, constipation, hair loss, sensitivity to heat or cold temperatures, mood changes, sweating, muscle aches, a fast heartbeat or weight changes)
- Damage to the liver (from inflammation) that does not cause symptoms, but does cause an abnormal result on a blood test of liver function
- Fever
- Anemia (low red blood cells that can cause tiredness, physical weakness or lack of energy)
- Dry mouth
- Headache
- Flu-like illness
- Swelling of an arm or leg
- Constipation
- Cough
- Shortness of breath
- Insomnia (trouble sleeping)
- Pneumonitis (inflammation of the lung) which may be life-threatening or may lead to death

- Abdominal pain
- Low white blood cells (that can make it more likely to get an infection)
- Chills
- Dry Skin
- Stomatitis (inflammation of mouth and lips)
- Decreased weight
- Dehydration
- Infusion reactions
- Muscle spasms
- Back pain
- Dizziness
- Low phosphate in the blood (that does not cause symptoms but causes an abnormal blood test)
- Blurry vision

Uncommon ($\leq 1\%$ of patients) but serious:

- Encephalomyelitis (inflammation of the brain), which may result in severe memory loss and occasionally death.
- Myasthenia gravis, a disease that causes muscle weakness
- Colitis, an inflammation of the colon
- Bronchospasm, a narrowing of air passages in the lungs causing shortness of breath
- Diabetic ketoacidosis, a severe complication of diabetes (high blood sugar) where the body makes too much acid in the blood.

As of January 2017, in all patients treated in all studies with Cemiplimab-rwlc, there were 5 deaths associated with Cemiplimab-rwlc. One patient died from encephalomyelitis (inflammation of the brain), one patient died from an unknown cause, two patients died from liver failure (including one with liver cancer), and one patient died from Toxic Epidermal Necrolysis (a type of severe skin reaction).

There are additional potential immune-related side effects from Cemiplimab-rwlc that may be serious and require corticosteroid treatment and interruption or discontinuation of treatment. While some of these side effects have been seen in patients treated with Cemiplimab-rwlc (also listed above), these side effects have been observed with other drugs that act on the immune system in a similar way. It is important to contact your doctor immediately if you experience any of these symptoms:

- Pneumonitis (inflammation of the lung): new or worsening cough, chest pain, or shortness of breath.
- Colitis (inflammation of the colon): diarrhea, blood in stool or severe abdominal pain
- Hepatitis (inflammation of the liver): jaundice (yellowing of skin, mucus membranes or whites of eyes), severe nausea or vomiting, or easy bruising or bleeding
- Hypophysitis (inflammation of pituitary gland which secretes hormones to control several body processes): persistent or unusual headache, extreme weakness, dizziness or fainting, vision changes, or other changes due to an effect on your hormones

- Nephritis (inflammation of the kidney): pain in pelvis, pain or burning during urination, frequent urination, blood in urine, vomiting, fever
- Hyperthyroidism and Hypothyroidism (over or underactive thyroid gland): tiredness, weight gain or loss, hair loss, constipation, depression, irritability, muscle aches, intolerance to heat or cold
- Uveitis (inflammation of the eye): eye redness, eye pain, light sensitivity, blurred vision, floaters, decreased vision
- Skin changes: peeling of the skin over large areas of the body, rash, itching, skin blistering.
- Mucositis (painful inflammation and ulceration of mucous membranes lining the digestive tract): painful sores in the mouth, tongue, nose or throat which can make it hard to eat or drink
- Encephalitis (inflammation of the brain): headache, fever, tiredness, confusion, memory problems, sleepiness, seeing or hearing things that are not really there, seizures, stiff neck

ALLERGIC REACTION RISK:

There is a chance of an allergic reaction to the study drug. Low levels of doxycycline, an antibiotic, are used early in the manufacturing process of Cemiplimab-rwlc. The possibility exists of an allergic reaction in patients allergic to doxycycline.

2.3.2 KNOWN POTENTIAL BENEFITS

Cemiplimab-rwlc is one of the PD-1 inhibitors with the most efficacy and safety data in management of unresectable locally advanced or metastatic cutaneous SCC.⁴ With Cemiplimab-rwlc as a monotherapy in patients with metastatic CSCC, overall complete response rate is 7% and partial response rate is 41%. Based on these efficacy and safety data, Cemiplimab-rwlc is now FDA approved for the treatment of patients with metastatic CSCC or locally advanced CSCC who are not amenable to curative surgery or curative radiation.¹³ However, there is no efficacy data in any immunocompromised population due to exclusion of these patients in clinical trials using PD-1 inhibitors. This population specific data are required to fulfill the unmet need.

3 OBJECTIVES

Primary Objective: Determine the overall response rate of Cemiplimab-rwlc in immunocompromised patients with unresectable locally recurrent and/or metastatic CSCC.

Secondary Objective:

1. Evaluate progression-free survival
2. Evaluate overall survival
3. Evaluate acute and late toxicities

Exploratory Objective:

1. Identify potential biomarkers related to response to Cemiplimab-rwlc in immunocompromised patients with unresectable locally recurrent and/or metastatic CSCC.

2. Evaluate overall response rate of underlying CLL in the CLL subset.

4 STUDY DESIGN AND ENDPOINTS

4.1 DESCRIPTION OF THE STUDY DESIGN

This is a single arm phase II study to evaluate the efficacy of Cemiplimab-rwlc in immunocompromised patients with unresectable locally recurrent or metastatic CSCC.

Eligible patients will be given Cemiplimab-rwlc 350 mg IV every 3 weeks. This will be administered until patients get severe side effects, disease progression, or for a period of 1 year (whichever point is reached first).

A scan will be performed approximately every 9 weeks till the time that the patient is receiving the treatment. We plan to recruit 27 patients.

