7.3.3 TREATMENT VISITS

On Treatment Visits

Study participants will be seen every 3 weeks before each cycle (Cycle 1 Day 1, Cycle 2 Day 1, etc).

In each scheduled visit we will:

- Obtain vital signs.
- Record all concomitant medication use.
- Perform a comprehensive physical examination.
- Obtain laboratory tests.
- Assess for AEs and SAEs.
- Assess compliance with the medication.
- Assess survival.
- Collect research blood sample (Cycles 3, 6, 9 and 12 only)
- Cemiplimab administration

Diagnostic imaging

Diagnostic imaging of affected and suspected sites (CT, MRI and/or photographs) will be done at Day 1 of cycles 3, 6, 9, 12, and 15 (or between Day 15-21 of the prior cycle) in all patients. Diagnostic imaging will continue to be done every 2 months thereafter or as clinically indicated otherwise.

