7.3.4 END OF TREATMENT VISIT

An End of Treatment (EOT) visit will be performed for all subjects. At the end of treatment (30 days after last Cemiplimab-rwlc dose) the following data will be collected:

- Obtain vital signs.
- Record all concomitant medication use.
- Perform a comprehensive physical examination.
- Obtain laboratory tests.
- Assess for AEs and SAEs.
- Assess compliance with the medication.
- Assess survival.
- Optional fresh tumor biopsy (in order to accommodate scheduling, this biopsy may occur up to an additional 30 days beyond the EOT visit).
- Diagnostic imaging of affected and suspected sites (CT, MRI and/or photographs), if not performed within the last 8 weeks.
- Collect research blood sample

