7.3.5 FOLLOW-UP

To assess for late toxicities, at 6 months and 12 months after EOT patients will return for a physical exam and labs, unless the patient has enrolled in hospice care or is otherwise unwilling/unable to return to clinic.

For this protocol, all patients, including those who discontinue protocol therapy early, will be followed for response until progression and for survival for 2 years from the start of treatment. All patients must also be followed through completion of all protocol therapy. Patients removed from study for unacceptable adverse events will be followed until resolution or stabilization of the adverse event. Follow-up for survival will be performed every 90 days (\pm 2 weeks) from the end of treatment visit.

Research blood collection to be performed at the end of study (2 years after initiation of study treatment).

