7.3.7 SCHEDULE OF EVENTS TABLE

Table 3. Schedule of events

Phase	Screen	Experimental phase																	EOT ^k	Follow-Up	
		1	2	3	4	5	6	7	8	9	10	11	12	13	14	15	16	17			
Cycle (21 days)	0																				
Day ^a	-28 to -0	1	1	1	1	1	1	1	1	1	1	1	1	1	1	1	1	1	30	Q3 months	
Assessments																					
Informed consent ^b	X ^c																				
Inclusion/exclusion	X ^c																				
Demographic data	X ^c																				
Medical history	X ^c																				
ECOG	X ^c																				
Vital signs ^d	X ^c	X ^c	X	X	X	X	X	X	X	X	X	X	X	X	X	X	X	X	X ^m		
Physical exam ^e	X ^c	X ^c	X	X	X	X	X	X	X	X	X	X	X	X	X	X	X	X	X ^m		
Laboratory tests ^f	X ^c	X ^c	X	X	X	X	X	X	X	X	X	X	X	X	X	X	X	X	X ^m		
Pregnancy test ^g	X ^c																				
Imaging studies (CT/MRI) ^h	X ^c			X			X			X			X			X			X ⁱ		
Mandatory research blood collection	X			X			X			X			X						X	X ⁿ	
Tumor collection	Mandatory: - Archival Optional: - Fresh Tissue																		Optional: - Fresh Tissue		
Cemiplimab Administration		X	X	X	X	X	X	X	X	X	X	X	X	X	X	X	X	X			
Concomitant meds ^j	X	X		X			X			X			X			X			X		
AEs/SAEs ^j		Throughout																X			
Survival		Throughout																X		X	

a: Efforts should be made to conduct study visits on the day scheduled (\pm 3 days). Clinical and laboratory assessments may be conducted anytime within 72 hours prior to the scheduled visit, unless otherwise specified in the Schedule of Visits and Procedures.

b: Informed consent may be taken up to 8 weeks prior to C1D1.

c: The baseline assessment can be performed on Cycle 1 Day (C1D1), prior to treatment. Clinical and laboratory assessments are valid if obtained within 72 hours of baseline assessment.

d: Assessments will include vital signs (resting BP, HR, RR, and body temperature and weight. BP, HR, and RR will be obtained after subjects have been resting for 5 minutes.

e: Comprehensive physical examination (including a neurological evaluation).

f: Laboratory tests include: CBC w/differential, CMP, ALT, AST, magnesium, amylase, lipase, TSH, and if clinically indicated INR.

g: Serum or urine, in women of childbearing potential only.

h: Baseline images to include CT/MRI of head /neck/ chest/abdomen/pelvis and other areas of known disease or clinical measurements and/or photographs of superficial tumors. On treatment imaging will include only areas of known disease plus any areas of newly suspected disease.

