i: All concomitant prescription medications taken during study participation will be recorded on the case report forms (CRFs).

j: AEs/SAEs will be assessed during each visit clinically and based on laboratory data. Patients will be encouraged to report AEs/SAEs at the earliest recognition via the phone between the visits.

k: End of Treatment visit is to occur 30 days after the last dose of Cemiplimab-rwlc therapy ± 7 days. If the subject is unable or unwilling to return to clinic this visit can be conducted via a telephone call.

l: May be omitted if performed within the last 8 weeks.

m: Physical exam and labs required at 6 months and 12 months after EOT only to assess for late AEs, unless the patient has enrolled in hospice care or is otherwise unwilling/unable to return to clinic.

n: Research blood collection to be performed at the end of study (2 years after initiation of study treatment).

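### Sections 4.1 and Table 3 conflict with 7.3.3, 7.3.5 and 5.4.2 on tumour imaging after treatment, and no post-treatment scan interval is clearly set for patients who stop before cycle 15

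*Combined protocol and SAP*

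**What the plan says.** Two places confine scheduled imaging to treatment and the EOT visit:

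- Section 4.1: "A scan will be performed approximately every 9 weeks till the time that the patient is receiving the treatment".
- Table 3 (7.3.7), row "Imaging studies (CT/MRI) ^h": marks at screening, cycles 3, 6, 9, 12 and 15, and EOT, with none under Follow-Up. Note h describes baseline and on-treatment imaging only.

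The EOT scan is conditional. Section 7.3.4 asks for "Diagnostic imaging of affected and suspected sites (CT, MRI and/or photographs), if not performed within the last 8 weeks". On timing, note k says the "End of Treatment visit is to occur 30 days after the last dose of Cemiplimab-rwlc therapy ± 7 days", and it allows a telephone call instead if the patient cannot or will not attend.

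Three places point to continued tumour assessment:

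- Section 7.3.3: imaging "will be done at Day 1 of cycles 3, 6, 9, 12, and 15", then "Diagnostic imaging will continue to be done every 2 months thereafter or as clinically indicated otherwise". No end is stated.
- Section 7.3.5: all patients, early stoppers included, "will be followed for response until progression and for survival for 2 years from the start of treatment".
- Section 5.4.2 gives early stoppers the same follow-up for response.

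The contacts that 7.3.5 actually schedules are survival checks every 90 days, an exam with labs at 6 and 12 months after EOT, and research blood at 2 years. It names no tumour assessment. Section 10.4.3 reports PFS as a Kaplan-Meier median with a 95% confidence interval and gives no censoring rule.

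**The concern.** Treatment is capped at 1 year and follow-up runs to 2 years. Patients who finish treatment, or who stop for toxicity, without having progressed are the ones still at risk of a progression event after EOT. If they are not scanned, progression is dated when it becomes clinically apparent, or is missed and the patient is carried as progression-free. Both errors lengthen apparent PFS, which is the first secondary endpoint.

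Six sites enrol. If some work from the schedule of events and others from 7.3.3, PFS is ascertained on different schedules within one 27-patient cohort. A response that first appears after an early stop could also go unrecorded, although 7.3.5 promises to look for it.

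**Working it through.** **Calendar.** Cycle k Day 1 = day 1 + 21(k − 1), from the 21-day cycle in Table 3.

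- Cycle 15: 1 + 21 × 14 = day 295. Cycle 17, the last dose: 1 + 21 × 16 = day 337.
- EOT: 337 + 30 = day 367, or 367/30.44 = 12.06 months. End of study: day 730.
- From the cycle 15 scan to EOT is 367 − 295 = 72 days (10.3 weeks). This exceeds 8 weeks, so a completer's EOT scan is due unless another was done in between.

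**Completers, scans after EOT to day 730.**

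- Following 4.1 and Table 3: 0.
- Following 7.3.3, every 61 days from day 295: days 356, 417, 478, 539, 600, 661 and 722. Six of these fall after day 367. As a check, (730 − 367)/61 = 5.95.

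**Early stoppers.** The word *thereafter* in 7.3.3 follows cycle 15, so it sets no clear interval for a patient who never reaches cycle 15.

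- Last dose at cycle 3 (day 43, when the first scan is due): EOT is day 73, 30 days after that scan, so EOT imaging may be omitted. The remaining gap is 730 − 43 = 687 days, over 22 months.
- Last dose at cycle 8 (day 148): EOT is day 178, 72 days after the cycle 6 scan (day 106), so a scan is due. The remaining gap is 730 − 178 = 552 days, about 18 months.

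**How many progressions fall after EOT.** The protocol gives no PFS median. I assume exponential PFS, S(t) = 0.5^(t/median), with all events being progressions. The share of events by month 24 that fall after EOT is [S(12.06) − S(24)] / [1 − S(24)].

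| Assumed median (months) | S(12.06) | S(24) | Patients progressing after EOT, by month 24 | Share of events by month 24 | Of 27 patients |
|---|---|---|---|---|---|
| 9 | 0.395 | 0.157 | 23.8% | 28% | 6.4 |
| 12 | 0.498 | 0.250 | 24.8% | 33% | 6.7 |
| 15 | 0.573 | 0.330 | 24.3% | 36% | 6.6 |
| 18 | 0.629 | 0.397 | 23.2% | 38% | 6.3 |

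**Effect on the planned median.** If progression after EOT is detected d months late, a true median beyond month 12.06 reads as the true median plus d. For a true median of 15 months, d = 1, 2 and 4 gives 16, 17 and 19 months. A delay of 1 month is also roughly what 2-monthly scans produce on average. For true medians of 9 or 12 months the curve crosses 50% before EOT, so completers' missing scans do not move it.

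**Primary test.** With 27 patients, P0 = 0.15, P1 = 0.33 and rejection at 7 or more responses, the exact binomial gives a one-sided level of 0.0986 and power of 83.8%, as in 10.5. No input to that calculation depends on the imaging schedule.

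**The case against.** The strongest reply is that 7.3.3 already supplies the scans. Only 42 days of treatment remain after cycle 15 Day 1 (337 − 295), so a 2-monthly scan first falls due about day 356, after the last dose. The sentence therefore reads most naturally as follow-up imaging. Section 4.1 is a short design summary, and 7.3.5 and 5.4.2 both expect assessment up to progression. This stands for completers. A reader might infer that PFS is largely unmeasured from month 12, but the documents support that only if 4.1 and Table 3 override 7.3.3. The reply does not help patients who stop before cycle 15.

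A reader might also infer that Table 3 ends imaging with the last dose. It does not, because it includes the conditional EOT scan. A blank Follow-Up cell is weak evidence on its own: in the text I worked from, the exam and laboratory marks carrying note m sit under EOT, although that note requires those procedures 6 and 12 months later. The conflict rests more firmly on 4.1, on note h and on the absence of any tumour assessment in 7.3.5.

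Progression can also be picked up without a scheduled scan, through clinically indicated imaging, the two late exams, or visible lesions measured by caliper. This shortens the delay but puts it on no defined schedule.

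Finally, the effect can be made to look larger by quoting a 24-month PFS rate. With a 12-month median and a 4-month delay it would read 31% (0.5^(20/12) = 0.315) instead of 25%. Section 10.4.3 plans no such rate, and the 4-month delay is a single assumed value, so I do not rest the point on it.

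**Conclusion.** The contradiction is real and should be resolved. Post-treatment ascertainment of PFS is undefined: completers have 0 or about 6 scans after EOT depending on the section followed, and early stoppers without progression have no clear interval under any section.

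If 4.1 and Table 3 are followed, 28% to 38% of progressions by month 24, in about 23% to 25% of patients, fall where no scan is scheduled. This assumes exponential PFS with medians of 9 to 18 months. Deaths would still be dated by the survival contacts, so the affected share is smaller to the extent that PFS events are deaths.

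The bias in PFS is upward. It reaches the planned median mainly if the true median exceeds about 12 months (15 months would read as 16 to 19 with a delay of 1 to 4 months), or if many patients stop early without progression.

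A reader might infer a material bias in the response rate. The documents do not support that: completers have five on-treatment scans plus EOT, so any effect is confined to responses first appearing after an early stop. It is probably small, and I have not quantified it. The sample size and primary test stand.

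**What to change.** Reconcile 4.1, 7.3.3, 7.3.5 and Table 3, keeping them consistent with 5.4.2:

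- Delete the on-treatment limit on scans in 4.1.
- In 7.3.5 and in the Follow-Up column of Table 3, add tumour assessment (imaging, or caliper and photograph for superficial lesions) at the 2-month interval already in 7.3.3.
- Apply it from EOT until progression or the 2-year end of study to every patient who left treatment without progression, whatever the cycle at which they stopped. The 2-year end is a choice to be stated: 7.3.5 attaches that limit to survival and sets none for response.

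The cost is protocol wording plus up to about 6 assessments for each completer who stays progression-free. Section 7.3.3 already calls for these, and 7.1.2 lists imaging as standard of care. Early stoppers may need more, in proportion to their longer remaining follow-up. No dose or treatment rule changes.
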